Study Device Names	Investigational device: pressure guidewire system (including wire with high-fidelity sensor strains and unique paired portable display units) Model: 100 Sponsor: Zurich Medical Inc. Agent: Shandong Visee Medical Devices Co., Ltd. Control group device: pressure guidewire Model: C12008 Manufacturer: St. Jude Medical, China Agent: St. Jude Medical (Shanghai) Co., Ltd. Registration license number: 国械注进20143775272 Analyzer Express Model: 12711 Manufacturer: St. Jude Medical, China Agent: St. Jude Medical (Shanghai) Co., Ltd. Registration license number: 国食药监械(进)字2013第3211615
Indication For Use	For patients who need coronary angiographic examination and coronary interventional treatment, pressure guidewire system is indicated to calculate the patient's blood fractional flow reserve (FFR), and to assist the physicians to make clinical decisions.

Trial Design	This clinical trial uses a multi-center, prospective, single-subject design trial method, using St. Jude Medical's pressure guidewire and Analyzer Express as a control device. The subjects who met the criteria for this study will be registered with the central registration system after enrollment. The subject's fractional flow reserve of coronary artery stenosis will first be measured using investigational device and recorded, and then measured using control device and recorded. The safety follow-up period is 48 hours.
Number of centers	Trial is expected to be held simultaneously at 5 centers in mainland China.
Sample size	300
Trial duration	The overall duration of clinical trials includes the time of signing of clinical trial site's agreements with all participating hospitals, the time of review and approval of the ethics committee meeting and the post-meeting opinion rectification, filing time, the trial kickoff, the enrollment and the subject's FFR measurement, the data collection, statistics, summary report writing time, etc., and is expected to be 2 years.
Inclusion Criteria	
 1) Age 18 to 75 years old, gender-unrestricted, non-pregnant female; 2) Understand and be willing to sign an informed consent form; 3) Diagnosed with coronary heart disease; 4) Invasive ICA and FFR measurement are needed; 5) Visual coronary angiography showed at least one moderate stenosis lesion (diameter stenosis of 30% - 70%) on the coronary artery with diameter ≥ 2.5mm

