3.2 Content

This clinical trial is designed as a multi-center, prospective, single-subject design trial. The investigational device is Zurich Medical Pressure Guidewire System (including wire with high-fidelity sensor strains and unique paired portable display units) and the control device is St. Jude Medical's FFR measuring device, Pressure Guidewire and Analyzer Express. The subjects who met the criteria for this study will be registered by login to the central registration system after enrollment, and the investigational device will first be used to

measure the fractional flow reserve of coronary stenosis lesions, and then the measurement of the same lesions by using the control device will be recorded, and followed with a 48hr post operation follow-up. Control device's FFR (FFR_{pw}) will be used as a reference to statistically analyze Investigational device's diagnostic accuracy, sensitivity, specificity, positive predictive values, negative predictive values, and the Area Under the Curve (AUC) of Receiver Operating Characteristic (ROC). FFR_{ws} and FFR_{pw} will be used to analyze the consistency, also Passing-Bablok regression analysis, Bland-Altman deviation analysis, and Pearson correlation analysis of the FFR_{pw} and FFR_{ws} will be used to evaluate the success rate of the device. Through above analysis, the effectiveness of diagnosis coronary artery disease by using Zurich Medical's pressure guidewire system to measure fractional flow reserve (FFR) can be verified. The adverse event and device defect during the measurement can also be recorded.

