7.1 Trial Design

This study is multi-center, prospective, single-subject design clinical trial. Subjects that signed Informed Consent form (ICF) which was approved by the Ethics Committee (EC) will enter selection process. Subjects that meet all inclusion criteria and do not meet any of the exclusion criteria, are considered eligible to enroll in the clinical trial.

Coronary angiography is performed on subjects. The investigators combine angiographic images and subject's inclusion/exclusion criteria to confirm if the subject meets the trial requirements. The subjects who met the criteria for this study will be registered by login to the central registration system after enrollment, and the investigational device will first be used to measure the fractional flow reserve of coronary stenosis lesions, and then the measurement of the same lesions by using the control device will be recorded, and followed with a 48hr post operation follow-up. The investigational device measure FFR using the innovative 1-sensor method according to the product Instructions for Use (IFU), and the control device measure FFR through the conventional AO method according to the product Instructions for Use (IFU).

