7.1.3 Measures to Lessen and Prevent Bias

This clinical trial will use the following methods to lessen bias in trials.

Multi-center: Case samples from multiple centers are more representative than single centers, preventing systemic errors in a single center from biasing the trial results, and obtained conclusions are more credible. To reduce the operational differences between the investigational sites, investigators should be trained by uniform standard, and clear evaluation criteria should be adopted for the effectiveness indicators and safety indicators.

Control: This study is a single-subject design clinical trial. Subjects use investigational device then control device to complete FFR measurements, preventing factors that may affect efficacy judgment.

Investigator Training: Before the clinical trial begins, the auditor and the head of investigational site will provide training for investigators, so investigators will gain understanding and become familiar with the investigational device. Investigators should also have grasp on all new findings during the clinical trial that's related to the investigational device.

Clinical Trial Monitoring: Develop inspection plan. Sponsor appoints auditors to conduct regular on-site audit of investigational sites, ensure that all content of the research program is strictly observed, and the original data is checked for consistency with the contents on the EDC.

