7.1.4 Investigational Medical Devices and Controlled Medical Devices /

[figure not shown]
Control Methods

The ICA examination performed by qualified interventional cardiologist. After the informed consent form is signed, coronary angiography will be taken from different positions via standard operating procedures. After enrollment, and registration in the central registration system, investigator will first use investigational device to perform FFR measurement, then use control device to remeasure FFR of the same vessel. The interval between two measurements should be greater than 3 minutes. The pressure guidewire

and catheter should be flushed with saline. Nitroglycerin to be used to eliminate coronary artery spasm, and ATP are to be infused through the central vein (intermediate elbow or femoral vein) at 140-180 $\mu\text{gkg}^{-1}\text{min}^{-1}$ to place the coronary vessels in hyperemia state. FFR measurements should be performed by qualified, experienced, and trained physicians, primarily focus on stenosis that shows moderately stenotic lesions (diameter stenosis 30% - 70%) in vessels that's ≥ 2.5 mm in diameter. The FFR results from the investigational device and the control device are not be used as a reference basis for further stent therapy. See operational instruction below:

DIRECTIONS TO USE ZURICH PRESSURE GUIDEWIRE SYSTEM 1-SENSOR METHOD TO TAKE MEASUREMENTS:

- 1) Open the package using sterile techniques
- 2) Fill the coil with saline solution, using the flush port
- 3) Soak Guidewire in saline until calibration is complete
- 4) Gently detach the portable display unit from the tray
- 5) Carefully wipe and dry the proximal end of Guidewire and insert into Handle (see Figure 1 for proximal end location of Guidewire)
- 6) Open the portable display unit by lifting the screen. This turns on the portable display unit

[figure not shown]

- 7) Verify the Guidewire-handle connection status icon is  displayed in the upper left corner to confirm the correct connection

- 8) Ensure the tray containing the Guidewire is at the same height as the patient's heart
- 9) Press the button  once for calibrating the system to zero atmospheric pressure (the

button is on the back of the screen). **CAL** will be displayed in the action state box at bottom center of the display

- 10) Carefully remove the Guidewire from the package coil

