WARNING: Guidewire is a delicate instrument and should be handled carefully. Bending or excessive force during removal from packaging tray may damage the guidewire.

CAUTION: If recalibration is necessary during the case, remove Guidewire from the body and follow the RESET procedure after step 20.

NOTE: After calibration, the Guidewire may be disconnected from the Portable Display for ease of advancement.

- 11) Engage the guiding catheter using standard practice and flush the catheter with sterile saline solution

WARNING: When introducing the Guidewire, confirm that the catheter tip is free within the vessel lumen and is not touching the vessel wall. Failure to do so may result in vessel trauma upon Guidewire exit of the catheter. Use the radiopaque marker of the catheter to confirm position.

- 12) Carefully insert the distal tip of the guidewire into the hemostatic valve of the Y connector. Advance Guidewire out of the guiding catheter and steer Guidewire to a location just proximal to the lesion of interest

- 13) Pull back the insertion tool out of the hemostatic valve and tighten the hemostatic valve

- 14) If the Guidewire has been detached from the Portable Display, carefully wipe and dry the proximal end and reconnect it now with the Handle. Verify the connection by checking for  in the upper left corner of the display

- 15) If estimating FFR, induce maximum hyperemia using standard clinical practice

CAUTION: Failure to achieve maximum coronary and myocardial hyperemia may result in invalid FFR.

- 16) Save the pressure proximal to the lesion of interest by pressing and holding the **BUTTON**

 until **SAV** is displayed in the action status box. At this point **RELEASE** the **BUTTON** 

- 17) Advance Guidewire across the lesion and perform pressure measurement

WARNING: Observe all Guidewire movements. Whenever Guidewire is moved or torqued, the tip movement should be examined under fluoroscopy.

WARNING: Torque Guidewire against resistance or repeated attempts to cross a total vessel occlusion may cause damage and/or fracture, which may lead to a portion of Guidewire separating from the tip.

CAUTION: Do not measure pressure when the sensor element of Guidewire is in sharp curves, since this might result in pressure artifacts.

NOTE: When a position of interest is difficult to reach, Guidewire may be disconnected from the Portable Display for easier use. Carefully wipe and then dry the male connector before reconnecting to Handle.

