[figure not shown]

[figure not shown]

Diagram 3: Live Data Screen 1-Sensor Method

- 18) Double-click the BUTTON  to begin recording an episode. **REC** will display in the action status box;
- 19) Press the  BUTTON again to once to end recording an episode. The data review screen of the episode will appear on the display. The two lowest FFR values will be displayed

[figure not shown]
20) Press the BUTTON  again once to return to live data screen;

WARNING: Excessive manipulation when sensor element or tip of Guidewire is located in sharp bend may cause damage or tip fracture. If the guiding catheter is in an anatomically severe or sharp bend, for example a tortuous subclavian artery or adjacent vessel position, the junction between the shaft and the flexible distal section of the wire, 31 cm from the tip, may be vulnerable to kinking or fracture.

DIRECTIONS TO RESET

NOTE: If for any reason, the Portable Display needs to be reset and returned to out-of-the-box settings, do the following

1. Press and hold the BUTTON  for more than 5 seconds until the RESET screen appears

2. Press the BUTTON  again to confirm reset to out of the box settings
3. If an inadvertent BUTTON  press for more than 5 seconds occurs, wait until the countdown clock reaches 0 and the portable display will return to the screen before the reset mode is activated

WARNING: Recalibration is required following RESET. Remove Guidewire from the body and follow the instructions above to calibrate.

Use St. Jude Medical 's Fractional Flow Reserve (FFR) Measuring Device to Measure FFR:

- 1) Connect the power cord, connect the aortic pressure input cable, and turn on the Analyzer Express
- 2) Select or create a new patient
- 3) Engage the guiding catheter in accordance with standard procedures and flush the

guiding catheter

- 4) Place the AO sensor at the same height as the patient's heart, connect the pressure sensor to the air (through the atmosphere), and zero the aortic pressure;
- 5) Open the pressure guide wire package and leave the pressure guide wire in the tray
- 6) Fill the packaging coil with heparin saline through the innermost rinse port of the packaging coil
- 7) Connect the pressure guidewire to the Analyzer Express, and zero the pressure guidewire
- 8) Gently remove the pressure guidewire from the packaging coil
- 9) Insert the pressure guidewire into the guiding catheter and advance the pressure guidewire until the pressure sensor just outside of the guiding catheter

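### Device order is fixed (investigational first, control second), so the Bland-Altman bias estimates device plus order; other secondary estimates share the problem to a lesser or unquantified degree

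*Combined protocol and SAP*

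**What the plan says.** Every place that sets the order gives the same one.

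- Section 7.1: "the investigational device will first be used to measure the fractional flow reserve of coronary stenosis lesions", with the control device second.
- Protocol Summary, Trial Design: FFR "will first be measured using investigational device and recorded, and then measured using control device and recorded".
- Section 3.2: investigational device first, "and then the measurement of the same lesions by using the control device will be recorded".
- Section 7.1.4: "investigator will first use investigational device to perform FFR measurement, then use control device to remeasure FFR of the same vessel".
- Section 7.1.5 (7) repeats that the control measurement comes after the investigational one.

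Section 7.1.3 lists the sequence among the measures against bias: "Subjects use investigational device then control device to complete FFR measurements, preventing factors that may affect efficacy judgment".

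Section 7.1.4 contains the safeguards between runs. "The interval between two measurements should be greater than 3 minutes"; wire and catheter are flushed with saline; nitroglycerin is given against spasm; each wire is zeroed separately. The control directions (step 15) also require a pull-back check that the two mean pressures agree within 3 mmHg.

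No section randomises, alternates or counterbalances the order, or repeats a run with the same device. Section 8 contains no order or period term. Section 7.1.6 computes the secondary accuracy, agreement and device-success endpoints from these ordered pairs.

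**The concern.** Pairing within a subject removes differences between subjects. It does not remove differences between a first and a second run. The second run follows an earlier hyperaemic induction in a vessel that has already been wired once. If either matters systematically, the effect always falls on the same side of the comparison. A real device bias could then be masked, or an order effect reported as device bias. More subjects would not help, because a larger sample only estimates the same mixture more precisely. Device success has a related problem: each device's rate comes from one position in the sequence only.

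**Working it through.** **1. Identification.** Let δ be the device difference and π the first-minus-second-run effect.

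- Investigational first: expected difference (investigational minus control) = δ + π.
- Control first: expected difference = δ − π.

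Under the plan only the first line is observed. The design matrix for (δ, π) has rank 1, so only the sum can be estimated. With both orders the rank is 2 and the two separate.

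**2. The plan's own precision (section 8.2.1).** Half-width for sensitivity: 1.96 × √(0.86 × 0.14 / 100) = 0.068. For specificity: 1.96 × √(0.78 × 0.22 / 200) = 0.057. Both match the stated ±6.8% and ±5.7%.

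**3. Bland-Altman bias.** Inputs: 300 subjects less 10% drop-out (section 8.2.1) = 270, taken as one vessel each; difference SD 0.05 is assumed. SE = 0.05/√270 = 0.0030, half-width 1.96 × SE = 0.006. With no device bias, the chance that the 95% interval excludes zero is Φ(π/SE − 1.96) + Φ(−π/SE − 1.96):

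| Order effect (FFR) | π/SE | Chance of excluding zero |
|---|---|---|
| 0.002 | 0.66 | 10% |
| 0.005 | 1.64 | 38% |
| 0.01 | 3.29 | 91% |

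**4. Sensitivity and agreement.** Assumed model: true FFR normal; independent, equal device errors; one third of control readings ≤0.80 (the 1:2 ratio in section 8.2.1); a constant shift on the first reading; no device bias. Exact bivariate normal probabilities over nine SD pairs (FFR SD 0.06, 0.08, 0.10; difference SD 0.03, 0.04, 0.05) give:

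| Shift | Change in sensitivity (points) | Change in agreement (points) |
|---|---|---|
| −0.02 | +7.8 to +12.5 | −3.8 to −1.6 |
| −0.01 | +4.4 to +7.0 | −1.2 to −0.5 |
| +0.01 | −8.6 to −5.0 | −0.3 to +0.3 |
| +0.02 | −18.1 to −10.4 | −1.6 to +0.1 |

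The fair yardstick is sampling error at each pair's own unshifted sensitivity (68% to 87%). With 100 positives the half-width there is 6.5 to 9.1 points. At ±0.01 the change is below it in eight of nine pairs; the exception is FFR SD 0.06 with difference SD 0.03 (8.6 against 7.9). At ±0.02 it is above it in all nine.

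**5. Remaining endpoints.** At FFR SD 0.08 and difference SD 0.05, a ±0.01 shift moves specificity by 3 to 4 points, PPV by under 4 and NPV by 2. The Passing-Bablok intercept is extrapolated to FFR 0 and estimated much less precisely than the bias (half-width roughly ±0.05 in simulation at these SDs), so shifts of this size would rarely show there. AUC, Pearson r, the slope and the width of the limits of agreement do not change under a constant shift. The documents allow no figure for device success.

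**The case against.** The strongest reply is that no order effect is documented. Its size, its direction and both SDs are assumptions, and the 91% figure falls quickly for smaller effects. The interval, flush, nitroglycerin, hyperaemia induced in each device's own procedure, separate zeroing and pull-back check all work to reduce an effect. None of the affected secondary endpoints has a pass rule. All of this stands and limits the weight of the point. It does not answer the identification problem: the safeguards may shrink an order effect, but nothing in the design can show that it is absent.

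The second reply is that randomising brings a bias of its own. The investigational operator chooses when to save the proximal reference (step 16: "Save the pressure proximal to the lesion of interest by pressing and holding the") and when to start and stop recording, and in half the subjects would do so knowing the control value. This is a real cost. The present order has the mirror problem: the control reading is always taken after the investigational result has been shown (step 19: "The two lowest FFR values will be displayed").

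Third, randomising mainly repairs the bias estimate. The effect on pooled primary agreement is unchanged, and on the same grid pooled sensitivity still moves by up to 6.7 points at ±0.02. Device also remains tied to method, since section 7.1 assigns the 1-sensor method to one device and the AO method to the other. These limits stand too.

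A reader might infer that the fixed order undermines the primary test. The documents do not support that. For a device with no bias of its own, ±0.02 moves agreement by −3.8 to +0.1 points, against the 8-point gap between 83% and 75%. The range is wider (−6.7 to +2.7) if the model is instead fitted to section 8.2.1's 86% sensitivity and 78% specificity. That fit needs a built-in device bias of −0.017 to −0.029, and the 0.02 order effect remains an assumption.

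**Conclusion.** The point holds as one of identification. With one order in every subject and no order term, the Bland-Altman bias is device plus order, and section 7.1.3 should not present the sequence as preventing distortion. The bias is the most exposed estimate. Sensitivity would be moved beyond its sampling error at a shift of 0.02 FFR, but mostly not at 0.01. The other affected endpoints are touched less, or by an amount that cannot be stated.

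All sizes rest on assumed SDs and assumed shifts, and the true effect could be negligible. A reader might also infer that an order effect is present or favours one device; nothing in the documents shows either. This is a cheap improvement to the secondary evidence and not a defect in the primary decision rule.

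**What to change.** 1. At the existing central registration, assign device order 1:1 at random, blocked by centre. Keep the existing interval rule.
2. Report the Bland-Altman bias with a period term. Report agreement, sensitivity, specificity and device success pooled and by order. State that pooled sensitivity is not fully corrected, and that by-order sensitivity has a half-width of about ±10 points: 1.96 × √(0.86 × 0.14 / n) is 0.096 at n = 50 positives per order and 0.101 at n = 45.
3. Keep the FAS and Safety Set of section 8.9 for the primary analysis, in line with the principle in section 8.8 that the analysis set is not modified. Report by order the subjects in whom only the control wire was used, including their safety data. Count them as inconsistent only in a sensitivity analysis.
4. If the order is kept, remove the claim in section 7.1.3 and state in the analysis plan and report that these secondary estimates cannot separate device from order.

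Cost: a protocol amendment with ethics approval (section 12.2) and an allocation field in the registration system, whose allocation capability is not described. No extra subjects, wires or procedures are needed, and the precision of the bias is unchanged. The downsides are that the investigational reading follows a known control reading in half the subjects, and that device and method stay confounded. Item 4 alone costs a few sentences.

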7.1.1 Trial Objective

To Evaluate the effectiveness and safety of Zurich Medical's pressure guidewire system (including guidewire with high-fidelity sensors and a unique paired portable display unit), which is used to measure the coronary artery blood fractional flow reserve (FFR) to diagnose coronary heart disease, and the effectiveness and safety of to direct a catheter through a blood vessel. Including:

Effectiveness: Coronary artery Fractional Flow Reserve(FFR) measured by control device, St. Jude Medical's Pressure Guidewire and Analyzer Express (FFRpw) will be used as a reference to evaluate FFR measured by Investigational device, the Zurich Medical pressure guidewire system (including wire with high-fidelity sensor strains and unique paired portable display units) (FFRws)'s efficacy to diagnose coronary artery disease via diagnostic consistency, sensitivity, specificity, positive predictive values, negative predictive value, and Area Under the Curve (AUC) of Receiver Operating Characteristic (ROC). Meanwhile, Passing-Bablok regression analysis, Bland-Altman deviation analysis and Pearson correlation analysis of the FFRpw and FFRws will be used to evaluate the success rate of the investigational device.

Safety: The adverse events and device defects that occur during Zurich Medical's pressure guidewire system measurement of coronary arterial FFRws will be mainly evaluated.

